INVESTIGATIONAL PLAN

welloStationX™ Determination of Clinical Accuracy

Protocol Number: 3939002

Revision: 6

Original Protocol Issue Date: September 21, 2018

NCT#: NCT03758157

Sponsor: Wello, Inc.
[name]
[name]

CONFIDENTIALITY STATEMENT

This document contains trade secrets and commercial information that are privileged or confidential and may not be disclosed unless such disclosure is required by federal or state law or regulations. In any event, persons to whom the information is disclosed must be informed that the information is privileged or confidential and may not be further disclosed by them. These restrictions on disclosure will apply equally to all future information supplied to you which is indicated as privileged or confidential.

Table of Contents

WS-001 STUDY SYNOPSIS.....	2
PROTOCOL APPROVALS	4
WELLO, INC. REPRESENTATIVES	5
STUDY SPONSOR 5	
TEST SITES 5	
STUDY MONITOR 5	
LIST OF ABBREVIATIONS	6
1.0 INTRODUCTION.....	7
1.1 Study Purpose.....	7
1.2 Indications for Use	7
2.0 DEVICE DESCRIPTION	7
2.1 Risk Analysis	7
3.0 DESIGN OF THE CLINICAL STUDY.....	8
3.1 Study Design	8
3.2 Subject Sample	8
3.2.1 Subject SampleSize Justification	8
3.2.2. Subject Qualification: Inclusion/ Exclusion Criteria	9
3.2.3 Subject Recruitment	9
3.2.4 Subject Compensation	9
3.3 Study Procedures	10
4.0 STATISTICAL ANALYSIS PLAN	11
4.1 Primary Outcome Measures	11
4.2 Primary Outcome Analysis	11
4.3 Study Success Evaluation	11
4.4 Safety Analysis	12
4.5 Handling of Missing Data.....	12
APPENDIX A: INVESTIGATOR AGREEMENT	14
APPENDIX B: WELLOSTATIONX LABELING	16
APPENDIX C: REFERENCE THERMOMETER LABELING.....	17
APPENDIX D: STUDY MONITORING	18

WS-001 Study Synopsis

Title	welloStationX Determination of Clinical Accuracy
Protocol Number	WS-001

Investigational Device	welloStationX
Objective	
 • To evaluate clinical bias with stated uncertainty • To determine clinical repeatability.
Inclusion Criteria For All Patients	
 • Males or females • Age groups: 
 ○ 5 and up • Each subject or guardian must sign an informed consent form.
Exclusion Criteria For All Patients	Use of medications known to affect body temperature (for example, antipyretics, barbiturates, thyroid preparations, antipsychotics, etc.) within 3 hours of the test, or immunization within seven days of the test.
Study Design	The study is a multi-site study designed to enroll subjects to obtain temperature readings with the welloStationX and a reference thermometer. The data collected will be analyzed to determine clinical bias with stated uncertainty and repeatability of the welloStationX.
Study Procedures	All subjects will have their temperature taken 3 times with the WelloStation, a non-contact infrared thermometer. Another single temperature reading will be taken with a Welch Allyn oral thermometer.
Primary Endpoints	
 • Calculation of clinical bias with stated uncertainty • Calculation of clinical repeatability • Calculation of limit of agreement
Number of Patients	A minimum of 105 subjects.
Number of Sites	Three test sites plus individual home locations.

welloStationX Determination of Clinical Accuracy

Protocol Number: 3939002

PROTOCOL APPROVALS

Project Manager

Date

[name]
Wello, Inc.

Date

INVESTIGATOR APPROVAL

I have read and familiarized myself with this protocol and I agree to conduct the study as described.

Principal Investigator

Date

Wello, INC. REPRESENTATIVES

STUDY SPONSOR

The Clinical Study is sponsored by Wello, Inc. Overall responsibility for the study will be held by and questions regarding clinical and scientific conduct of the study should be addressed to:

[name]
Wello, Inc.
[name]
[name]
[name]
Office [contact]

TEST SITES

1. Wello Inc. Office
[name]
[name]
2. Agape Clinic
[name], Director of Services
[name]
[name]
3. Community Council
[name], EVP
[name]
[name]
4. Individual Homes located in Dallas, Ennis, Frisco and Plano, Texas

STUDY MONITORS

1. [name] – Community Council, September 28; Agape Clinic, October 3rd and October 4th
2. [name] – Agape October 5 and October 16th
3. [name] – Wello Offices and various residences

INSTITUTIONAL REVIEW BOARD (IRB)

IntegReview IRB
[name]
[name]
[contact]
Email: [contact]

LIST OF ABBREVIATIONS

C	Celcius
F	Farenheit
IRB	Institutional Review Board
ISO	International Standard

1.0 INTRODUCTION

1.1 Study Purpose

To determine the Clinical Accuracy of the welloStationX by:

- evaluating clinical bias with stated uncertainty; and
- determining clinical repeatability.

1.2 Indications for Use

The results of this clinical study are intended to support the following indications for use: ““The welloStationX is a non-contact device intended for use to measure the body temperature of individuals five years of age and older. The welloStationX can be used by medical professionals or laypersons in any public or private indoor facility including home use. The welloStationX has an ambient operating temperature range of 59F – 82.4F (15C – 28C).””

2.0 Device Description

The welloStationX is an automated No-Touch Self-Service Electronic Thermometer designed to provide an accurate temperature reading without the time and exposure of a skilled attendant to the possibility of infection.

The welloStationX is an electronic thermometer using an infrared sensor of the surface of the forehead adjusting human body skin temperature to oral thermometer without contact.

The welloStationX is being evaluated for use for the screening of individuals for fever.

Deatiled information on the configuration and operation of the welloStationX can be found in the accompanying welloStationX Use and Care Manual.

2.1 Risk Analysis

The general risks associated with the welloStationX device are relatively minimal based on a review of published literature and known safety issues associated with the use of these types of infrared thermometer devices.

Wello has taken steps throughout the manufacture and design of the welloStationX to reduce or eliminate all potential risks to the user. Wello has identified the potential risks and actions taken to address each risk below:

- The welloStationX is not intended to be used around water. Do not set up the welloStationX near a sink or other wet area. If it is necessary to place near a sink or other wet area, make sure the unit is plugged into a working GFCI outlet.

- Always operate the thermometer in an operating temperature range 16°C to 40°C (60.8°F to 104°F), and relative humidity less than 95%.
- Always store the welloStationX in a cool and dry place -20°C to 50°C (-4°F to 122°F) and relative humidity less than 95%.
- Do Not Attempt Repairs – Do not attempt to open, take apart, service or modify the product or power supply to avoid the risk of electrical shock. Any attempt to open or service the product will void the Limited Warranty.
- Important AC Adapter Safety
 - Use only the power supply units supplied with the unit.
 - Do not use non-standard sources for power such as generators or inverters. Only use standard AC power provided by a standard wall outlet.
 - Do not overload the wall outlet or power strip or extension cord.
 - Check AC plug to make sure the prongs are configured properly and are of the proper configuration for the wall adapter.
 - Ensure the power cord is not left in a position where it can be walked on, pinched, tripped over or otherwise pulled from the wall

3.0 DESIGN OF THE CLINICAL STUDY

3.1 Study Design

This is a non-randomized, non-blinded single arm study design with the subject as his or her own control to evaluate the clinical accuracy of the welloStationX thermometer in the screening of individuals with fever.

3.2 Subject Sample

Subjects will be males and females aged 5 years of age and older. A total minimum of 105 subjects will be enrolled with 32-52 of those subjects being febrile. For the purpose of this testing, fever is defined as a core temperature of 99.5°F (37.5°C) or higher.

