3.2.1 Subject Sample Size Justification

Subject sample size selection is based on the specifications in ISO 80601-2-56; 201.102.2: human subject population requirements: “The minimum number of subjects in the CLINICAL ACCURACY VALIDATION shall not be less than 105” and “The total number of febrile subjects shall be not less than 30% and not greater than 50% of all subjects in the selected age group.”

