The study was a non-randomized, non-blinded single arm design with the subject as his or her own control to evaluate the clinical accuracy of the welloStationX thermometer with respect to that of the standardized Welch Allyn SureTemp oral thermometer in the screening of individuals with fever.

4. Subject Sample

Subjects were 110 males and females aged 5 years of age and older: 33 subjects (30%) were febrile, with fever defined as a core temperature of 99.5°F (37.5°C) or higher; and 77 subjects were afebrile.

Subjects were recruited from amongst non-profit clinical sites and through social media posts for subjects to come to a test site or to be evaluated in his or her own home in the widespread Dallas/Fort Worth area.

Afebrile subjects were compensated with a \$10 gift card and febrile subjects were compensated \$25, the additional amount intended to assist the febrile subject to recovery.

5. Study Procedures

Each subject's temperature was measured three separate times sequentially using the study device, the WelloStationX® (*DUT*) and one time using a new off-the-shelf calibrated Welch Allyn SureTemp oral thermometer with disposable probe covers (the reference thermometer). Each measurement was recorded by a trained technician by following the instructions for use contained in the respective device labeling.

Subject age, gender and race were recorded for each subject, and potential adverse event observation was conducted.

A subject or the subject's guardian was immediately informed if a febrile temperature measurement (99.5°F (37.5°C) or higher) was recorded using the Welch Allyn SureTemp oral thermometer. The subject or guardian will be advised to consider seeking medical attention.

RESULTS

6. Sample Demographics

The sample demographics of gender, age and race are shown below in Tables 1 through 3, respectively, for febrile and afebrile subjects and for subjects overall.

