7.1 Means and Standard Deviations

Table 4 below shows the mean and standard deviation of temperature readings in °F with the welloStationX (DUT) and the Welch Allyn SureTemp (reference thermometer) by febrile versus afebrile subject groups.

Table 4: Means and Standard Deviations by Febrile Status

Temperature Reading (°F)	welloStationX Febrile (n=33)	Welch Allyn Febrile (n=33)	welloStationX Afebrile (n=77)	Welch Allyn Afebrile (n=77)
Mean	99.83	99.58	98.15	98.22
Standard deviation	0.60	0.71	0.47	0.29

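### The febrile quota is a fixed 32-52 with no upper limit on N, so its lower end misses the cited 30% floor from N=107; the reported 33 of 110 has no margin, and Table 4 puts that count in question

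*Protocol*

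**What the plan says.** Protocol section 3.2 gives an open-ended total and a fixed febrile count: "A total minimum of 105 subjects will be enrolled", "with 32-52 of those subjects being febrile". The synopsis repeats the minimum ("A minimum of 105 subjects"). Neither place gives a maximum N or a rule for rescaling the febrile count if more subjects are enrolled. Section 3.2 defines fever as a core temperature of 99.5°F or higher.

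Section 3.2.1 justifies the sample size wholly by a quoted standard. The total "shall not be less than 105", and the number of febrile subjects "shall be not less than 30% and not greater than 50% of all subjects in the selected age group". There is no power or precision calculation.

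The SAP document, which is the clinical results report, states in its section 4 that there were 110 subjects and that "33 subjects (30%) were febrile". Its Table 4 ("Means and Standard Deviations by Febrile Status") gives the Welch Allyn reference readings of the 33 febrile subjects as mean 99.58°F, SD 0.71, and the welloStationX readings as mean 99.83°F, SD 0.60.

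**The concern.** The working quota is a count and the rule behind it is a percentage. They agree at the minimum enrolment and drift apart above it. A study team could therefore keep to section 3.2 and still miss the requirement on which the whole sample-size justification rests.

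The study did enrol above the minimum, at a total where the two rules differ. The reported febrile count is the smallest that the percentage rule allows at that total. A net loss of one subject from the febrile group would take the share below 30%, and the printed summary of the febrile reference readings does not fit a group in which every oral reading reached 99.5°F. At stake is whether the cited requirement can be reported as met, and which subjects belong in the febrile and afebrile analyses that Protocol section 4.2 calls for.

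**Working it through.** **Inputs.** Minimum N 105 and febrile count 32-52 (Protocol 3.2); febrile share 30% to 50% (Protocol 3.2.1); achieved N 110, febrile 33 (report section 4); Table 4 means and SDs (report 7.1); bias definition and values (report 7.2).

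**1. Reproduce the quota.** Lower limit: 0.30 × 105 = 31.5, rounded up to 32. Upper limit: 0.50 × 105 = 52.5, rounded down to 52. This matches 32-52 exactly.

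**2. Hold 32-52 fixed and raise N.** The required range is 0.30N rounded up to 0.50N rounded down.

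| N | Required | 32/N | 52/N |
|---|---|---|---|
| 105 | 32-52 | 30.48% | 49.52% |
| 106 | 32-53 | 30.19% | 49.06% |
| 107 | 33-53 | 29.91% | 48.60% |
| 110 | 33-55 | 29.09% | 47.27% |
| 120 | 36-60 | 26.67% | 43.33% |
| 173 | 52-86 | 18.50% | 30.06% |
| 174 | 53-87 | 18.39% | 29.89% |

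The whole range complies only at N=105 and 106. From N=107 the lower end fails. Some counts in the range still comply up to N=173, and none from N=174. The upper limit of 52 stays under 50% throughout; above N=105 it is simply stricter than the rule.

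**3. The achieved sample.** 33/110 = 30.00%, which meets a floor of not less than 30%. 32/110 = 29.09%, which would pass section 3.2 and fail section 3.2.1.

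**4. Can 33 readings of at least 99.5°F have mean 99.58 and SD 0.71?** With a fixed mean and a lower bound, the SD is largest when 32 readings sit on the bound and one takes all the excess. The mean excess is 99.58 − 99.50 = 0.08, so the total excess is 33 × 0.08 = 2.64. Then SD² = [32 × 0.08² + (2.64 − 0.08)²]/32 = (0.2048 + 6.5536)/32 = 0.2112, so SD = 0.46, which equals 0.08 × √33. If the mean was rounded down from 99.585, the bound is 0.085 × √33 = 0.49. The printed 0.71 exceeds both.

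**5. Could the Table 4 columns be swapped?** With the columns exchanged, the febrile reference would be 99.83, SD 0.60. The mean excess is 0.33 and the bound is 0.33 × √33 = 1.90, so the conflict disappears. Report section 7.2 describes bias as reference minus device. From Table 4 as printed, that gives 99.58 − 99.83 = −0.25 (febrile) and 98.22 − 98.15 = +0.07 (afebrile). The bias table in 7.2 gives +0.25 and −0.06. Both signs are reversed. Swapped columns would explain this, but so would a misdescribed order of subtraction, and in that case the SD conflict in step 4 remains.

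**The case against.** The strongest reply is that section 3.2.1 directly follows section 3.2 and quotes the percentage rule, so 32-52 can be read as the worked count at the minimum enrolment. On that reading this is a drafting gap and not an arithmetic error. The reported study also met the rule on its own count, enrolment is over, and rewording the quota changes no result. At N=110 only one count in the range, 32, separates the two rules; at 31 or fewer both would fail. Much of this stands, and it limits the quota point to wording. It does not remove it, because the operative limit is written as a count, nothing says to rescale it, and enrolment went beyond the two totals at which it is safe.

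A reader might infer from Table 4 that at least one subject was certainly mislabelled as febrile. The documents do not support that as a fact. It requires that the Table 4 columns are labelled correctly, that the printed figures are right, and that the oral reading set febrile status. The reversed signs in report section 7.2 give a concrete reason to doubt the columns. The classifying reading is not stated: Protocol section 3.2 speaks of core temperature, no core measurement is described, and section 3.3.5 applies 99.5°F to the oral reading only for informing subjects. The Table 4 point is therefore a query with several possible answers. Even so, each answer calls for a correction or clarification somewhere.

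**Conclusion.** The fixed count does not carry the cited rule beyond N=106. At the achieved N=110 a count of 32 would satisfy section 3.2 and give 29.1% against a 30% floor. The defect is confined to the lower limit. A reader might infer that the whole 32-52 range fails away from N=105, or that the 50% ceiling is at risk; neither follows, since 33 to 52 all comply at N=110 and 52 never exceeds 50%. A reader might also infer that the study missed the requirement. On its reported count it did not: 33 of 110 is exactly 30.0%.

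That count has no margin, and Table 4 as printed cannot describe 33 oral readings of at least 99.5°F. One of these must hold: at least one febrile subject read below 99.5°F on the reference; febrile status was set by another reading; or Table 4 has swapped columns or a wrong figure. The documents do not show which. If the first holds, and no subject labelled afebrile read 99.5°F or higher on the reference, the share counted by the oral reading is at most 29.1%. The SD bound itself needs only the printed mean, n=33 and the 99.5°F limit, with no distributional assumption.

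**What to change.** - Protocol 3.2: replace the fixed count by at least 30% and at most 50% of all subjects analysed, with 33-55 shown as the count at N=110.
- State which reading assigns febrile status for the quota and the analyses under the protocol's own 99.5°F definition.
- Check Table 4 against the source data, and reconcile it with the subtraction order and signs in report section 7.2.
- Recount febrile status across all 110 subjects by the stated rule, so that moves in either direction are caught, and restate the percentage. If it is below 30%, report that the cited requirement was not met. If any subject changes group, rerun the results by febrile status.

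The cost is a wording change and a recount from data already collected. The downside for the sponsor is that the stated 30% may become less favourable.

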3.2.1 Subject Sample Size Justification

Subject sample size selection is based on the specifications in ISO 80601-2-56; 201.102.2: human subject population requirements: “The minimum number of subjects in the CLINICAL ACCURACY VALIDATION shall not be less than 105” and “The total number of febrile subjects shall be not less than 30% and not greater than 50% of all subjects in the selected age group.”

3.2.2. Subject Qualification: Inclusion/ Exclusion Criteria

Inclusion Criteria

All subjects must meet the following inclusion criteria to be eligible for the study:

- Male or female.
- Age group: 5 years and up.
- Each subject or guardian must sign an informed consent form.

Exclusion Criteria

Subjects meeting any of the following criteria will be excluded from the study:

- Use of medications known to affect body temperature (for example, antipyretics, barbiturates, thyroid preparations, antipsychotics, etc.) within 3 hours of the test.
- immunization within seven days of the test.

3.2.3 Subject Recruitment

Subjects will be recruited from amongst the following sources:

- Non-profit clinical sites, including a busy free clinic in downtown Dallas.
- Social media posts which will invite subjects to come to the Wello, Inc. office in suburban Dallas, or will offer home visits by study staff if located in far off metro areas of Dallas/Fort Worth.
- Social media posts offering free shared car service or a \$25 gift card for transportation if able to come to the centrally located sites.

3.2.4 Subject Compensation

Afebrile subjects will be compensated with a \$10 gift card and febrile subjects will be compensated \$25, the additional amount intended to assist the febrile subject to recovery.

3.3 Study Procedures

3.3.1 Demographics

Age, gender and race will be recorded for each subject.

3.3.2 Study Device Measurements

1. Each subject's temperature was measured three times sequentially using the study device, the welloStationX® (DUT).
2. Each measurement was recorded by following the instructions for use contained in the device labeling.
3. Each measurement was recorded by a trained techninian.

3.3.3 Oral (Reference) Thermometer Measurements

1. Each subject's temperature was measured one time using a new off-the-shelf calibrated Welch Allyn SureTemp oral thermometer with disposable probe covers.
2. Each measurement was recorded by following the instructions for use contained in the device labeling.
3. Each measurement was recorded by a trained techninian.

3.3.4 Adverse Events Evaluation

Throughout the four measurement recordings, any reported and/or observed adverse events will be recorded on the CRF and reported and dealt with applicably.

There are no reasonably anticipated adverse events with use of the welloStationX infrared thermometer.

3.3.5 Reporting of Febrile Temperature Recordings

A subject for whom a febrile temperature measurement (99.5°F (37.5°C) or higher) was recorded using the Welch Allyn SureTemp oral thermometer will be reported immediately to the subject or in the case of a minor, to the guardian. The subject and/or guardian will be advised to consider seeking medical attention.

4.0 STATISTICAL ANALYSIS PLAN

4.1 Primary Outcome Measures

The Primary Outcome Measures for this study are to evaluate:

1. Clinical Accuracy of the welloStationX; and
2. Clinical Repeatability of the welloStationX

4.2 Primary Outcome Analysis

As per ISO 80601-2-56, these measures will be recorded and analyzed as follows:

1. *Clinical Accuracy* will be evaluated by comparing the first recorded measurement using the welloStationX with the single measurement recorded by the Welch Allyn SureTemp oral thermometer.

Results will be presented through:

- (i) Descriptive presentation of means and standard deviations
- (ii) Evaluation of agreement calculated as the clinical bias (mean bias (\pm SD))
- (iii) Limits of Agreement (LOA) calculations
- (iv) Band-Altman plot created using mean bias and standard deviation data
- (v) XY Plot and Correlation Coefficient calculation

2. Repeatability will be calculated using the pooled standard deviations formula.

All analyses will be performed and presented by febrile status (febrile and afebrile) and by device (test device compared with reference device), as applicable.

4.3 Study Success Evaluation

Accuracy and reliability in welloStationX thermometer readings will be demonstrated if there is close agreement between the welloStationX and the reference device (Welch Allyn SureTemp oral thermometer).

Additionally, agreement values will be referenced against those attained for the prior validation study for the CareGiver thermometer, with agreement values for the welloStationX to be comparable or better to the published data for the Caregiver. This reference is the following:

**Clinical validation of the CAREGIVER[®] non-contact thermometer model
PRO-TF200/PRO-TF300 in febrile and afebrile patients of all ages**

Naja E. [name], Alice Huang & Gary O'Hara MSE

November 2013 Copyright ©2013 Thermomedics[®], Inc.

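### The success rule in Protocol 4.3 infers reliability from agreement with no condition on repeatability, a primary outcome, and its Caregiver benchmark lacks figures, a margin and a deciding metric

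*Protocol*

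**What the plan says.** Protocol section 4.1 lists two primary outcome measures: clinical accuracy, and "Clinical Repeatability of the welloStationX".

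Section 4.2 analyses them separately. Accuracy is assessed by "comparing the first recorded measurement using the welloStationX with the single measurement recorded by the Welch Allyn SureTemp oral thermometer". Under that item come "Evaluation of agreement calculated as the clinical bias" (mean and SD) and the limits of agreement. The second outcome has its own line: "Repeatability will be calculated using the pooled standard deviations formula". No acceptance limit is attached to it. Analyses are to be presented by febrile status.

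Section 4.3 is the only statement of what counts as success, and it has two parts. The first is "Accuracy and reliability in welloStationX thermometer readings will be demonstrated if there is close agreement between the welloStationX and the reference device". The second refers to the earlier Caregiver validation study, "with agreement values for the welloStationX to be comparable or better to the published data for the Caregiver". Repeatability is not mentioned in section 4.3, and no Caregiver figure is printed in the protocol.

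The Caregiver values appear only in the Discussion of the results report (filed as the SAP):

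- limits of agreement +0.82 and -1.21;
- overall bias up to 0.20°F, and 0.32°F in the afebrile group;
- repeatability 0.17 overall, 0.21 febrile and 0.15 afebrile.

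**The concern.** A primary outcome should be able to affect the verdict. Here the rule refers only to agreement and then claims reliability as well. The second and third device readings do not enter agreement at all, so a device could meet the written rule with repeatability worse than the predicate's.

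The agreement part is also loosely drawn. No figure defines close agreement, and no margin defines comparable. Section 4.2 names bias and limits of agreement, but section 4.3 does not say which decides, or whether it is judged overall or by febrile group. That choice can be made after the data are seen.

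What is at stake is the report's conclusion that the device is both accurate and reliable. If reliability covers repeatability, that half of the claim has no prespecified test behind it.

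**Working it through.** **Inputs, all from the results report**

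- Overall bias and SD of differences: 0.03 and 0.42°F, n = 110 (section 7.2).
- Limits of agreement: +0.86, -0.80 (section 7.3).
- Repeatability: 0.13 febrile (n = 33), 0.09 afebrile (n = 77), 0.06 overall (section 8; 0.062 in the Discussion).
- Caregiver figures: as listed above (Discussion).

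**1. Reproduce the reported limits.** 0.03 ± 1.96 × 0.42 gives +0.853 and -0.793. These match +0.86 and -0.80 within the rounding of the inputs.

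**2. Pool the repeatability.** √[(33 × 0.13² + 77 × 0.09²)/110] = 0.104°F, or 0.099 to 0.109 allowing for rounding. The reported overall 0.06 lies below both group values, which a pooled SD cannot do. I use 0.104 and give the result for 0.062 in step 6.

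**3. Share of the disagreement due to repeat error.** Assume repeat error is an independent, additive part of the first reading's error. Its share of the variance of the differences is 0.104²/0.42² = 0.0107/0.1764, or about 6%.

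**4. Caregiver width.** Half-width = (0.82 + 1.21)/2 = 1.015°F. Implied SD = 1.015/1.96 = 0.518°F.

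**5. Roughly double the repeatability SD, to 0.20°F.** This is worse than the Caregiver's 0.17. The SD of differences becomes √(0.42² - 0.104² + 0.20²) = 0.453. The half-width becomes 1.96 × 0.453 = 0.89°F, up from 1.96 × 0.42 = 0.82 and still inside 1.015.

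**6. Largest repeatability that keeps the limits no wider than the Caregiver's.** √[0.518² - (0.42² - 0.104²)] = 0.32°F. Using 0.062 in place of 0.104 gives 0.31. Varying the SD of differences over its rounding range (0.415 to 0.425), with 0.104, gives 0.31 to 0.33.

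**7. Does the choice of agreement metric matter?**

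| Metric | welloStationX | Caregiver | Better |
|---|---|---|---|
| Width of limits | 1.66 | 2.03 | welloStationX |
| Largest absolute limit | 0.86 | 1.21 | welloStationX |
| Overall bias (absolute) | 0.03 | 0.20 | welloStationX |
| Upper limit | +0.86 | +0.82 | Caregiver |

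The last row assumes that both studies use the same sign convention, which the documents do not establish. The report also sets this device's febrile bias (0.25) against the Caregiver's afebrile bias (0.32). Section 4.3 does not provide for comparing unlike groups in this way, and the documents do not give the Caregiver's febrile bias.

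**The case against.** **A reader might infer that no agreement result could fail.** The documents do not support that. The second part of section 4.3 sets a published benchmark, and agreement clearly worse than the Caregiver's would miss it. Steps 4 and 6 rely on that benchmark being failable. Nor is it right that no agreement metric is named: the synopsis and section 4.2 name bias and limits of agreement. What is missing is which of them decides, in which group and with what margin.

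**Reliability is not defined.** The documents do not equate it with repeatability, so reading it that way is an assumption. This does not remove the point, because section 4.3 has no repeatability condition under any reading.

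**Agreement does constrain repeatability.** The first reading carries repeat error, so the limits of agreement cap it. That is correct, but the cap is loose, at nearly twice the Caregiver's value.

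**The report did examine repeatability.** It compares all three values with the Caregiver's, and all are lower. The stated objectives are also to estimate bias and repeatability. Both points stand and limit the practical harm here: no reported value changes. But section 4.3 did not call for the repeatability comparison, so it is not part of the stated success rule.

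**Conclusion.** The concern holds as a fault in the stated rule. Section 4.3 can declare success whatever the repeatability result, provided agreement is satisfactory, although repeatability is one of two primary outcomes. Under independent additive error and the reported group values, repeatability could reach about 0.32°F (0.31 to 0.33 in the variations shown) against the Caregiver's 0.17 before the width of the limits became worse than the Caregiver's. That ceiling concerns width only; it says nothing about bias. It also treats the Caregiver figures as exact, because that study's sample size and uncertainty are not in the documents.

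The agreement benchmark is usable but underspecified, and step 7 shows that the answer can turn on the metric chosen.

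A reader might also infer that the device failed on repeatability or that the reported conclusion is wrong. The documents do not show this: 0.13 and 0.09 are below 0.21 and 0.15, and overall both the reported 0.06 and the recomputed 0.104 are below 0.17.

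**What to change.** Revise Protocol section 4.3 as follows.

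1. Delete the inference of reliability from agreement.
2. Add a repeatability condition: the pooled SD is to be no worse than the Caregiver's for the same group (0.17 overall, 0.21 febrile, 0.15 afebrile, as quoted in the report).
3. State that both bias and limits of agreement are compared with the Caregiver's, like group with like group, and print the values from the cited study. The documents do not give them all; the Caregiver's febrile bias, for example, is missing. Say whether the limits are judged by width or by largest absolute limit. Either give a margin for comparable or drop the word.
4. Require every part for success.
5. Report confidence bounds alongside as description. Making them the test would turn a no-worse rule into a superiority test against values treated as fixed. As description, the one-sided 95% upper bounds, SD × √(df/χ²₀.₀₅), are 0.152 febrile (df 66), 0.099 afebrile (df 154), and 1.96 × 0.473 = 0.93°F for the overall half-width (df 109).

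The cost is wording, retrieval of the cited values and a few calculations on existing data. The rule gains a condition that can fail. Because the results are already reported, it must be labelled post hoc for this dataset; it can be prespecified only for later work. The overall repeatability of 0.06 should be corrected or explained before it is used in the comparison.
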